17. References	78
18. Appendices.....	79
19. Version History.....	81

2. Glossary

Term	Definition
ADE	Adverse Device Effect
AE	Adverse Event
ASA	American Society of Anesthesiology
BIS™	Bispectral Index (BIS) technology monitoring uses processed EEG signals to measure sedation depth based on the level of consciousness
CFR	Code of Federal Regulation
CIP	Clinical Investigation Plan
CNS	Central Nervous System
CO ₂	Carbon Dioxide. It can be measured with a capnograph, a device that measures the concentration of carbon dioxide from each inspired and expired breath. Gases are collected with a non-invasive side stream from the inhaled and exhaled gases of the subject. Capnograph outputs numeric values and waveforms of the fractionated concentration of CO ₂ of each breath
CRF	Case Report Form
CTA	Clinical Trial Agreement
CV	Curriculum Vitae
DD	Device Deficiency
DoH	Declaration of Helsinki
DTL	Delegated Task List
ECG	Electrocardiogram. A diagnostic tool that measures and records the electrical activity of the heart
eCRF	Electronic Case Report Form
ED	Effective dose
EDC	Electronic Data Capture. Electronic systems where the data are collected through the eCRF (Oracle Clinical). May also be referred to as RDC (Remote Data Capture).
EEG	Electroencephalogram

Medtronic Business Restricted

Term	Definition
ET	End-tidal concentration
EMR	Electronic Medical Record
EtCO ₂	End-tidal Carbon Dioxide. The value of exhaled carbon dioxide displayed by the capnograph device
FD	Financial Disclosure
FDA	Food and Drug Administration
GCP	Good Clinical Practice
HIPAA	Health Insurance Portability and Accountability Act
HR	Heart Rate
ICF	Informed Consent Form
IFU	Instructions for Use
IRB	Institutional Review Board
ISF	Investigator Site File
LMA	Laryngeal mask
LOC	Level of consciousness
NSR	Non-Significant Risk
PHI	Protected Health Information
PI	Principal Investigator
PIC	Patient Interface Cable
PK/PD	Pharmacokinetics and pharmacodynamics
RA	Regulatory Authority
SAE	Serious Adverse Event
SAP	Statistical Analysis Plan
SpO ₂	A non-invasive spectroscopic estimate of arterial oxygen saturation measured transcutaneously by a pulse oximeter

Medtronic Business Restricted

Term	Definition
SOC	Standard Of Care
SOP	Standard Operating Procedures
SQI	Signal Quality Index
UADE	Unanticipated Adverse Device Effect

3. Synopsis

Title	Bispectral Index and End Tidal Anesthetic Gas Concentration in Pediatric Patients undergoing Sevoflurane Anesthesia (BTIGER)
Clinical Study Type	Post-Market Pivotal /IDE Study
Product Name	BIS™ Complete Monitoring System
Sponsor	Medtronic, Patient Monitoring & Respiratory Interventions [name]
Indication under investigation	Intended for use in pediatric patients (4 years old and above)
Investigation Purpose	The purpose of this study is to investigate the relationship between BIS™ values including EEG profile and anesthetic agents in the pediatric population
Product Status	BIS™ is commercially available in the United States
Primary Objective(s) and/or Endpoint(s)	Primary objective: To characterize BIS™ performance with the anesthetic agent in pediatric patients ages 4 to 18 years Primary endpoint: The end-tidal sevoflurane concentration in both patient groups acquired during maintenance of anesthesia. The study will be considered a success if the primary objective, achieving statistical and clinical significance in obtaining the end-tidal sevoflurane concentration during maintenance in both patient groups, is achieved.
Secondary Objective(s) and/or Endpoint(s)	Secondary endpoint(s): 
Recovery assessments in patients receiving monitoring compared to standard anesthetic practice (instructions for collection contained in Study Procedures and Assessments):

Medtronic Business Restricted

	
• Emergence• Emergence is defined as the time when any of the following first occurred:
• Eyes open spontaneously• Crying or phonating• Purposeful movements• PACU discharge readiness using Modified Aldrete Score [15,16]• Anesthesia Airway Management (AAM) will be noted:
○ Awake and Deep Extubation (endotracheal tube (EET) vs. laryngeal mask airway (LMA)○ Airway reflexes (e.g., coughing, choking, laryngospasm) 
Additional/Exploratory Endpoints:
 
• Clinical Anesthesia Assessment, recorded as the incidence of movements, grimacing, eye opening, tearing, sweating, mydriasis and cardiovascular changes while undergoing anesthesia• Pediatric Anesthesia Emergence Delirium (PAED)• Wong-Baker FACES Pain Rating Score
Study Design	
This is a multi-center, prospective, observational, non-invasive, randomized controlled study to collect data to compare the performance of standard practice (SP) group with the BIS™ monitoring (BIS) group. Pediatric patients between the ages of 4 to 18 years undergoing routine sevoflurane general anesthesia with an expected maintenance duration of greater than 30 minutes will be recruited. If the maintenance duration is less than 25 minutes, the data will continue to be collected, but will not be included in the data analysis and the subject will be replaced with an additional subject. General surgeries including abdominal, urological, orthopedic, ophthalmological or other procedures approved by the Medtronic study team with an American Society of Anesthesiologists physical status of I - III. Children will be recruited from the preoperative clinic and will be divided into three age groups
 
• 4 to 8 years• 9 to 12 years

Medtronic Business Restricted

- 13 to 18 years

A training group comprising of the first 2 - 4 subjects at each site will be enrolled to train the site team on the new technology and to determine the quality of data collection prior to randomization. Afterward, randomization will proceed based on the Sponsor's assessment of data quality.

For the BIS™ group, sevoflurane will be titrated to achieve a target BIS™ value of 45 – 60 during maintenance of anesthesia and a target BIS™ value of 60 – 75 beginning at the start of skin closure. In order to protect against inadequate or excessive anesthesia in the BIS™ guided group, the subject will be assessed approximately every 5 minutes for signs of anesthesia. In the event of hypertension and/or tachycardia (>20% above baseline) unexplained by surgical manipulation and or signs of autonomic or somatic responses (e.g., diaphoresis, movement) an additional dose of opioid will be administered. If that does not resolve the situation, then the anesthesiologist may alter the anesthetic concentration outside the BIS™ guidelines to assure adequate anesthesia. In the event of hypotension and/or bradycardia (>20% below baseline), fluids and/or vasopressor will be administered. If that does not resolve the situation, then the anesthesiologist may alter the anesthetic concentration outside the BIS™ guidelines. Subjects with BIS™ values that are outside of the specified range of 45 – 60 during maintenance of anesthesia for >35% of the maintenance duration will be considered a protocol deviation and the subject will be excluded from the final data analysis. The subject will be replaced by an additional enrolled subject. The excluded subject will continue to be monitored for any safety events and the clinician will ensure medical care is provided for any safety event that occurs. Data from excluded subjects will be acknowledged in the final study report but will not be included in the primary statistical analysis. The exception to this exclusion is any data that is outside of the specified range of 45 – 60 as a result of the anesthesiologist titrating sevoflurane as a result of clinical signs or cardiovascular changes defined above. The end-tidal sevoflurane concentration will be continuously recorded. Fentanyl or morphine will be administered at the discretion of the anesthesiologist, for example, 1.5 mcg/kg at induction and 0.75 mcg/kg every 30 minutes in accordance with usual clinical indications.

For the SP group, sevoflurane, fentanyl, propofol, and morphine will be administered at the discretion of the anesthesiologist for example, fentanyl and morphine at 1.5 mcg/kg at induction and 0.75 mcg/kg every 30 minutes in accordance with usual clinical indications.

Medtronic Business Restricted

Randomization	Subjects will be randomized 1:1 within each age group and each site to one of the two groups, standard practice (SP) or BIS™ (BIS) groups.
Sample Size	The first 2 - 4 subjects at each site will be enrolled to train the site team on the new technology and to determine the quality of data collection prior to randomization (n = 16-32). They will not be randomized and will not be included in the final analysis. For the analysis, a minimum of 36 subjects are required in each age group (18 per treatment group) for a minimum of 108 qualifying data sets. Subjects with non-qualifying data sets will be rejected and replaced with a newly randomized subject. This sample size was independently powered for each of the 3 age groups based on data from a previously published study conducted by Emory University.
Planned number of sites	Eight investigational sites in the US
Inclusion/Exclusion Criteria	
Inclusion Criteria:
 
1) Pediatric Subjects (ASA PS I or II or III) aged: 4 years to 18 years scheduled for procedures with sedation where the process of assessment will not interfere with the procedure, progress, or patient care 
Exclusion Criteria:
 
1) Has severe contact allergies that may cause a reaction to standard adhesive materials found in pulse oximetry sensors, ECG electrodes, respiration monitor electrodes, or other medical sensors2) Known neurological disorder (e.g., epilepsy, the presence of a brain tumor, a history of brain surgery, hydrocephalic disorders, depression needing treatment with anti-depressive drugs, a history of brain trauma, hemiplegia, demyelinating disorders, cerebral palsy, congenital anomalies of the brain or spinal cord, or other known neurologic disorders)3) Severe developmental delay per assessment of investigator or report of parent/guardian4) Airway abnormalities5) Pregnancy; subjects of childbearing potential will have a urine screen for pregnancy before surgery6) If the process of assessment will interfere with the procedure or the progress of the procedure7) Taking psychoactive medications

Medtronic Business Restricted

	
8) Taking any medications that may have an impact on the Central Nervous System (CNS)
 
9) Planned use of any regional anesthesia; a local field block is not included in this exclusion and can be used at the discretion of the anesthesia provider
 
10) Planned use of dexmedetomidine (Precedex)
 
11) Refusal to participate in the study

Study Procedures and Assessments	
BIS™ Group:
 
Baseline/Enrollment Visit:
 
• Informed Consent• Review of Inclusion/Exclusion• Demographics• Medical History• Pre-operative vitals obtained in pre-operative holding 
Procedure:
 
• Randomization: Prior to Procedure• Induction and Maintenance:• BIS™ sensor positioning and validation of appropriate impedance of electrodes• Clinical Anesthesia Assessment including incidence of:
• Movement• Grimacing• Eye opening• Tearing• Sweating• Mydriasis• Cardiovascular changes• End of Procedure:
• Collection of BIS™ sensor placement, monitoring of cardiovascular variables, event markers and assessments• Recovery:

- Anesthesia Airway management
- Collection of incidents of post- op nausea
- Pediatric Anesthesia Emergence Delirium (PAED)
- Wong-Baker FACES Pain Rating Score when subject is awake
- Time of PACU Discharge

SP Group:

Baseline/Enrollment Visit:

- Informed Consent
- Review of Inclusion/Exclusion
- Demographics
- Medical History
- Pre-operative vitals obtained in pre-operative holding

Procedure:

- Randomization: Prior to Procedure
- Induction and Maintenance:
- BIS™ sensor positioning and validation of appropriate impedance of electrodes
- Clinical Anesthesia Assessment including incidence of:
 - Movement
 - Grimacing
 - Eye opening
 - Tearing
 - Sweating
 - Mydriasis
- Cardiovascular changes
- BIS™ monitor concealing: done to ensure that the clinician is blinded to the BIS™ values and that the BIS™ value is not used to guide the conduct of the anesthetic. The signal quality index (SQI) number will be visible to the anesthesiologist during the case to capture a good quality signal. The details on SQI monitoring will be provided to the study site.

- End of Procedure:
 - Collection of BIS™ sensor placement, monitoring of cardiovascular variables, event markers and assessments
- Recovery:
 - Anesthesia Airway management
 - Collection of incidents of post- op nausea
 - Pediatric Anesthesia Emergence Delirium (PAED)
 - Wong-Baker FACES Pain Rating Score when subject is awake
 - Time of PACU Discharge

Prior to induction

The subjects will be taken into the operating room, and anesthesia delivery system will be applied per institutional guidance. Prior to the induction of anesthesia, all subjects will have an age-appropriate BIS™ sensor applied. The clinician will select the appropriate BIS™ pediatric or BIS™ QUATRO sensor based on the size and space available on the subject's forehead. The sensor will be placed on the forehead per the IFU recommendation. If the patient is not cooperative when awake, the BIS™ sensor will be placed after adequate sedation has been achieved with the use of pre-medication drugs. The choice of pre-medication, dose, and time of administration will be determined by the site anesthesiologist and will not be altered for this study, but the use of these drugs will be recorded on the eCRFs.

In addition, an age-appropriate pulse oximeter sensor (reference 7.5.1) will be applied to the patient per sensor IFU. A left or right index finger is the preferred sensor site. Alternatively, the sensors can be applied to a smaller finger, thumb, or big toe. The sensor type, position, and side will be recorded on the eCRFs.

Monitoring and Cardiovascular Variables

Pulse oximeter, non-invasive blood pressure (NIBP), electrocardiography, and skin temperature will be collected per institutional guidance but are not mandated per the protocol. The standard monitoring procedures will be conducted per institutional recommendation. The de-identified digital copies of these files will be provided to Medtronic as available.

Medtronic Business Restricted

Pre-surgical Cardiovascular variables (heart rate [HR]; systolic and diastolic blood pressure [BP] including hypotension; oxygen saturation; and temperature), and the BIS™ value (for the BIS™ group) will be recorded at baseline preferably before administering any pre-medication or sedatives. Cardiovascular variables will be monitored during the surgery, and any abnormal hemodynamic parameters and times will be noted. The de-identified digital copies of these files will be provided to Medtronic as available.

Induction

Anesthesia will be induced with sevoflurane alone, or a combination of sevoflurane and nitrous oxide (N₂O) in 100% oxygen for both groups. If nitrous oxide is used, it will be discontinued after the placement of a tracheal tube or laryngeal mask (LMA), or another airway management. If necessary, a neuromuscular blocking agent will be used to facilitate endotracheal intubation. The choice of induction medication, dose, and time of administration will be determined by the site anesthesiologist and will not be altered for this study, but the use of these drugs will be recorded on the eCRFs. If the subject is in need of a nerve block for pain management following the procedure, this block should be placed once skin closure is complete and prior to extubation. This block cannot be placed prior to skin closure. Subjects with the planned use of any regional anesthesia are excluded from this study, however if a caudal block becomes necessary for the subject during the course of the surgical procedure, data will continue to be collected on the subject, however the data will not be included in the data analysis and the subject will be replaced by an additional enrolled subject. The use of dexmedetomidine (Precedex) is prohibited from being used in this study. If it becomes necessary to use this medication during the course of the surgical procedure, data will continue to be collected on the subject, however the data will not be included in the data analysis and the subject will be replaced by an additional enrolled subject.

Maintenance anesthesia

In the SP group, sevoflurane, fentanyl, and morphine administration will be at the discretion of the anesthesiologist, for example, fentanyl

Medtronic Business Restricted

and morphine 1.5 mcg/kg at induction and 0.75 mcg/kg every 30 minutes, using clinical signs and cardiovascular changes to adjust anesthetic concentration.

In the BIS™ group, fentanyl and morphine administration will be at the discretion of the anesthesiologist, for example, fentanyl and morphine 1.5 mcg/kg at induction and 0.75 mcg/kg every 30 minutes, using clinical signs and cardiovascular changes, however sevoflurane will be adjusted to achieve a target BIS™ values of 45 – 60 during maintenance of anesthesia and BIS™ values of 60 – 75 beginning of skin closure. Subjects with BIS™ values that are outside of the specified range of 45 – 60 during maintenance of anesthesia for >35% of the maintenance duration will be considered a protocol deviation and the subject will be excluded from the final data analysis and will be replaced by an additional subject. The excluded subject will continue to be monitored for any safety events and the clinical will ensure that medical care is provided should a safety event occur. Data from the excluded subject will be acknowledged in the final study report but will not be included in the primary statistical analysis. The exception to this exclusion is any data that is outside of the specified range of 45 – 60 as a result of the anesthesiologist titrating medications as a result of clinical signs or cardiovascular changes defined above. Additionally, data points will be excluded if significant artifact is present or if the sevoflurane concentration or BIS™ value is missing.

At the completion of the surgery, and after confirmation of the return of neuromuscular function, sevoflurane will be discontinued, and discontinuation time will be recorded, and as applicable, extubation will be performed when the patients demonstrate the purposeful movement, facial grimace, or eye-opening to jaw thrust.

Event Markers and Assessments

During the case, the time of events (for example start of induction, LOC, airway management /intubation (as applicable), the start of the procedure, incision, N₂O off (as applicable), sevoflurane off, extubation (as applicable), eye-opening, end of the procedure, move to PACU, and PACU discharge readiness) will be recorded.

	
The end-tidal anesthetic gas concentration will be time-locked to the BIS™ system recordings. End-tidal sevoflurane, oxygen, and nitrous oxide concentrations will be downloaded from the anesthetic monitoring device, and de-identified digital copies will be provided to Medtronic.
 
Time and values of BIS™, ET_{SEVO} concentration (%) and other medication, FiO₂(%) and EtO₂(%), EtCO₂(%) will be recorded at the following time intervals:
 
• Baseline• Study start• At IV placement, as applicable• Start of induction• Start of N₂O, as applicable• Start of sevoflurane• Anesthesia Airway Management (AAM)• AAM change (including type of AAM)• At any airway reflex (coughing, choking, layngospasm)• Every 15 min after airway management• At all medication administration (as applicable)• N₂O off (as applicable)• Start of the surgery/procedure• Skin incision, if applicable• End of surgery/procedure (or skin dressing or cast or splint applied or abdominal block)• Skin closure, if applicable• Sevoflurane off• Termination of all anesthesia• Extubation• Physician Awakening subject, if applicable• Time of emergence (if occurs in OR)• End of study (removal of device)
--	---

	
• 15 min post dexmedetomidine administration, if applicable• Time moved to PACU 
Recovery Assessments
 
Subject recovery will be observed continuously after the termination of anesthesia for presence of coughing, choking, laryngospasms, and emergence. Emergence is defined as the time when any of the following first occurred:
 
• eyes open spontaneously,• crying or phonating, or• purposeful movements. 
The time of emergence, time subject moved to PACU, and time of readiness for discharge will be recorded. The time of these assessments will be captured in medical records, source, and recorded on the eCRFs.
 
All subjects will be assessed at 15-minute intervals beginning at anesthesia termination:
 
• Vitals Signs• Pediatric Anesthesia Emergence Delirium (PAED)• Wong-Baker FACES Pain Scale (when subject is awake)• PACU discharge readiness - Modified Aldrete Score
Safety Assessments	
This is a prospective, randomized, controlled study where the only change in routine management is the placement of the BIS™ monitor probe on the forehead. The choice of sedative drugs, dose, and route of administration will be based on clinical indications as judged by the attending Anesthesiologist, and it will not be changed for the study.
 
The BIS™ monitor will not be used in situations where the placement of the probe will interfere with a procedure, cause scan artifacts, or where the presence of a metal monitor is contraindicated (e.g., MRI scans). Therefore, we believe there is only a minimal increase in risks from participating in the study. This risk relates to the possibility of developing irritation to the skin at the site of placement.

	
Subjects will be monitored for Adverse Events, Serious Adverse Events, and Device-Related Adverse Events from BIS™ sensor applications throughout the BIS™ sensor removal.

Statistics	
Standard demographic information and baseline characteristics will be summarized using descriptive statistics. For safety assessments, adverse events (AEs) will be summarized using frequency counts and percentages. Descriptive statistics will be provided by severity and relationship as needed.
 
The primary analysis will be based on all evaluable data (excluding training subjects). Normality of data will be tested using the Kolmogorov-Smirnov test. Depending on whether normality assumption hold, a two group t-test or Wilcoxon rank-sum test will be used to compare between the two treatment groups. A P-value of less than 0.05 is considered statistically significant unless otherwise specified.
 
The secondary endpoints will be evaluated using the Holm-Bonferroni method to ensure the overall type I error rate is controlled at the 0.05 level.
 
Cardiovascular Variables will be summarized for both groups. The incidence of hypotension will be summarized and compared to anesthesia sedation levels.
 
The anesthetic requirements with the BIS™ value, the percentage of time during maintenance with BIS™ values within the specified ranges, and number of episodes and duration of burst suppression will be assessed for both treatment groups.
 
Additional endpoints, including PAED scale, Pain Rating Score and a subgroup analysis for subjects requiring neuromuscular blockade, will be summarized using descriptive statistics for each group and groups combined.

4. Introduction

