10.9.6 Recovery

Subject recovery will be continuously after the termination of anesthesia for presence of coughing, choking, laryngospasms, and emergence.

Emergence is defined as the time when any of the following first occurred:

- eyes open spontaneously,
- crying or phonating, or
- purposeful movements.

The time of emergence, time subject moved to PACU, and time of readiness for discharge will be recorded. The time of these assessments will be captured in medical records, source, and recorded on the eCRFs.

All subjects will be assessed at 15-minute intervals:

- Pediatric Anesthesia Emergence Delirium (PAED)
- Wong-Baker FACES Pain Scale (when subject is awake)
- PACU discharge readiness - Modified Aldrete Score

PAED, Wong-Baker FACES Pain Scale, and Modified Aldrete Score data will be recorded in source every 15 minutes. Raw data but total scores for the highest amount of delirium from the PAED, the highest amount of pain from the Wong-Baker FACES Pain Scale and the least ready for discharge Modified Aldrete Score raw data will be entered in to the CRF. The final raw data and total scores for the PAED, Wong-Baker FACES Pain Scale and Modified Aldrete Scale will be entered into the eCRF.

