10.9.6.2 Pediatric Anesthesia Emergence Delirium (PAED)

Both groups will be assessed using the Pediatric Anesthesia Emergence Delirium (PAED) scale [1]. The PAED is an observational scale that has been validated in children to detect and measure the severity of hyperactive emergence delirium upon awakening from anesthesia. The scale includes 5 items: 1) Child makes eye contact with the caregiver, 2) child's actions are purposeful, 3) child is aware of his/her surroundings, 4) child is restless, 5) child is inconsolable. The scale is included in **Appendix A**. The time and treatments/conmedications given for delirium and will be documented.

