Appendix A – Pediatric Anesthesia Emergence Delirium (PAED) [1]

The PAED Scale	
Item scores are added together for a total score, with higher scores indicating more severe delirium	
Items 1,2,3 are scored as follow: 4 = not at all 3 = just a little 2 = quite a bit 1 = very much 0 = extremely	Items 4 and 5 are scored as followed 0 = not at all 1 = just a little 2= quite a bit 3 = very much 4 = extremely
Items	Sore
1. Child makes eye contact with caregiver	
2. Child's actions are purposeful	
3. Child is aware of his/her surroundings	
4. Child is restless	
5. Child is inconsolable	
Total Score	

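### PAED is scheduled from the end of anesthesia with no awake condition and the highest score is kept, so any rating taken before emergence can put a floor of 12 of 20 on that child's recorded peak

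*Protocol*

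**What the plan says.** The Recovery Assessments part of the protocol synopsis gives the schedule: "All subjects will be assessed at 15-minute intervals beginning at anesthesia termination". The list beneath it contains vital signs, PAED, Wong-Baker and the Modified Aldrete Score. One line carries a condition: "Wong-Baker FACES Pain Scale (when subject is awake". The PAED line has none.

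Section 10.9.6 has the same contrast between the two scales but gives no starting point: "All subjects will be assessed at 15-minute intervals". It keeps all 15-minute ratings in source and sends two PAED values to the case report form. One is the worst: "total scores for the highest amount of delirium from the PAED". The other is the last: "The final raw data and total scores for the PAED, Wong-Baker FACES Pain Scale and Modified Aldrete Scale will be entered into the eCRF".

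Appendix A scores the first three items (eye contact, purposeful action, awareness of surroundings) in reverse: "Items 1,2,3 are scored as follow: 4 = not at all". The other two (restless, inconsolable) run the usual way: "Items 4 and 5 are scored as followed 0 = not at all". The items are summed, and a higher total means worse delirium.

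Section 10.9.6.2 describes the scale as measuring the "severity of hyperactive emergence delirium upon awakening from anesthesia". It does not say when rating starts or what to do with a child who has not woken.

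Protocol 14.1 and SAP 7.9 have PAED summarized descriptively and compared between groups. Neither says whether the highest or the final value is meant.

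**The concern.** The schedule, the scoring key and the peak rule are each reasonable alone but do not fit together. A child who is still anesthetized makes no eye contact, shows no purposeful action and is not aware of the surroundings. The key gives full points for all three. Once such a rating is in the series, taking the maximum carries it into the eCRF unless a worse rating follows.

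PAED is the only delirium scale in the trial. If many first ratings precede emergence, the recorded peaks pile up at 12, and differences between children below that level are lost. The sites are also left to choose. A rater who follows the synopsis literally records 12, while a rater who waits for awakening departs from the written schedule. If they choose differently, the peaks are not comparable across sites.

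**Working it through.** The documents give no PAED value for a child who has not emerged, so there is no stated figure to reproduce. The check has three parts.

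**1. Score before emergence.** From the Appendix A key:
- calm, unresponsive child: 3 × 4 + 2 × 0 = 12
- scale maximum: 5 × 4 = 20

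Recorded peak = max(awake peak, 12) for any child with such a rating.

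**2. Effect if every child is rated at time zero.** Protocol 4.1.3.1 cites peak PAED of 7.7 (SD 4.6) and 8.6 (SD 5.3) from a randomized trial of light against deep anesthesia. These values stand in for awake peaks; the distribution shape is an assumption, so three were tried. For the continuous normal, with z = (12 − m)/s, the share at or below 12 is Φ(z), and the mean recorded peak is 12 + s[φ(z) − z(1 − Φ(z))].
- m = 7.7: z = 4.3/4.6 = 0.93; share 82.5%; mean 12.43
- m = 8.6: z = 3.4/5.3 = 0.64; share 73.9%; mean 12.84

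| Assumed shape | Peaks recorded as 12 (7.7 / 8.6) | Mean recorded peak | Difference |
|---|---|---|---|
| Normal, continuous | 82.5% / 73.9% | 12.43 / 12.84 | 0.40 |
| Normal, rounded, clipped to 0–20 | 85% / 77% | 12.42 / 12.80 | 0.38 |
| Beta-binomial on 0–20, same mean and SD | 82.9% / 74.0% | 12.51 / 12.95 | 0.44 |

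Without the floor the difference is 8.6 − 7.7 = 0.9. Across shapes, about 74–85% of peaks sit at 12 and the difference falls to about 0.4.

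**3. Effect if the first rating is at 15 minutes.** Table 3 of protocol 4.1.3.2 (ages 3–18) gives time to first response of 7.0 (SD 3.9) minutes for SP and 4.2 (SD 3.7) for BIS. The share not yet responsive at 15 minutes is:
- SP: normal, z = (15 − 7.0)/3.9 = 2.05, 2.0%; lognormal with the same mean and SD, 4.2%
- BIS: normal, z = (15 − 4.2)/3.7 = 2.92, 0.2%; lognormal, 2.0%

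These times run from the end of the procedure. The protocol records termination of anesthesia as a separate event, so they are indicative only.

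**The case against.** The strongest reply is that the large figures need a rating at the moment anesthesia stops. That starting point is in the synopsis only. Section 10.9.6 gives none, and the synopsis wording can also mean that the clock starts then and the first rating falls 15 minutes later. On that reading almost no child is affected. This stands, and it is why the size must be given as a range.

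A reader might infer that the recorded peak measures unconsciousness and not delirium. The documents do not support that. A later score above 12 still becomes the peak, and the final PAED is entered as well. The final value is simply the last rating, however, so it cannot replace the peak.

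A reader might also infer a bias that favors BIS, because SP children woke later in the reference study. If all children are rated at time zero, both arms share the same floor and the effect is compression. If all are first rated at 15 minutes, hardly anyone is on the floor. A bias by arm needs first ratings in between, or timing that varies, and the documents give no distribution of rating times. It is possible but cannot be sized.

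It can also be said that 10.9.6.2 ties the scale to awakening, that 10.9.6 asks for the worst delirium and not merely the largest number, and that Wong-Baker needs the child's own answer whereas PAED is observed. Raters may therefore wait without being told, and the case report form guidelines, which are not among these documents, may say so. Table 5 does not settle it: its end-of-surgery column also marks Wong-Baker, which is for awake subjects only. These points make harm less certain, but none of them is a rule for a child not yet awake.

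The stakes are limited. PAED is exploratory, has no success criterion, and treatment given for delirium is documented separately.

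**Conclusion.** The defect is real but confined to one exploratory endpoint. Followed literally, the synopsis schedule, the Appendix A key and the peak rule give a calm child rated before emergence a recorded peak of at least 12 of 20, above both mean peaks the protocol cites. The share of peaks fixed at 12 runs from about 74–85% (all rated at time zero) to about 0.2–4% (first rating at 15 minutes). The upper range rests on awake peaks resembling the cited trial and on an assumed shape. The lower range rests on first-response times from the reference study, with its different clock. If timing varies, the floor could fall more often on the arm that wakes later, by an amount the documents do not allow one to estimate. The primary endpoint and its power are unaffected. The plan should be corrected because a stated rule yields a wrong score and the remedy is cheap.

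**What to change.** - In the synopsis recovery list, 10.9.6 and 10.9.6.2, give PAED the same awake condition that Wong-Baker has, on the existing 15-minute schedule. A separate rating at emergence is not needed.
- Record PAED as not assessable at any time point before the recorded emergence time.
- In SAP 7.9, name the peak PAED, derived only from ratings after emergence, as the value compared between arms, with the final PAED also reported.
- Before database lock, re-derive peaks already collected from the 15-minute ratings in source and the emergence time.

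The cost is minor rewording of the protocol, the eCRF instructions and the SAP, plus the re-derivation. Some children will have fewer PAED ratings.
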